11.3 Institutional Review Board

This study is being conducted under a United States IND application. This protocol (and any modifications) and appropriate consent procedures must be reviewed and approved by an IRB/IEC. This board must operate in accordance with the current federal or local regulations. The Investigator will send a letter or certificate of IRB/IEC approval to Kadmon Corporation (or designee) before subject enrollment and whenever subsequent modifications to the protocol are made.

11.4 FUTURE USE OF SUBJECT SAMPLES

Not all of the tissue and blood components obtained during this study may be required for the tests that are part of the clinical trial. Following the conclusion of the study, the samples may be used for additional research. This research will help to understand disease subtypes, drug response and toxicity, and possibly identify new drug targets or biomarkers that predict subject response to treatment. The use of the samples for internal research will be done according to the guidelines defined by the FDA guidance for In Vitro Diagnostic Device Studies Using Leftover Human Specimens that are Not Individual Identifiable (issued April 25, 2006) and/or the European Medicines Agency Reflection Paper on Pharmacogenetic Samples, Testing and Data Handling (EMEA/CHMP/PGxWP/201914/2006). If a subject requests destruction of their tissue and blood samples and the samples have not yet been de-identified, Kadmon Corporation will destroy the samples as described in this FDA guidance. Kadmon Corporation will notify the Investigator in writing that the samples have been destroyed. Once all samples have been analyzed for additional research, the samples will be discarded and will not be stored for future research.

12. CONDITIONS FOR MODIFYING THE PROTOCOL

Protocol modifications will be reviewed and approved by Kadmon Corporation representatives.

All protocol modifications must be submitted to the IRB/IEC for information and approval in accordance with local requirements, and to regulatory agencies if required. Approval must be obtained before any changes can be implemented, except for changes necessary to eliminate an immediate hazard to study subjects, or when the change involves only logistical or administrative aspects of the trial (e.g., change in monitor, change of telephone number).

13. CONDITIONS FOR TERMINATING THE STUDY

Kadmon Corporation has the right to terminate the study at any time. In terminating the study, Kadmon Corporation and the Investigator will ensure that adequate consideration is given to the protection of the subjects' interests.

14. STUDY DOCUMENTATION, CRFS AND RECORD KEEPING

14.1 INVESTIGATOR'S FILES AND RETENTION OF DOCUMENTS

The Investigator must maintain adequate and accurate records to enable the conduct of the study to be fully documented and the study data to be subsequently verified. These documents should be classified into 2 separate categories as follows: (1) Investigator's study files and (2) subject clinical source documents.

The Investigator's study file will contain the protocol and protocol amendments, eCRFs, query forms, IRB/IEC, and governmental approval with correspondence, sample ICF, drug records, staff curriculum vitae and authorization forms, and other appropriate documents and correspondence.

Subject clinical source documents (usually predefined by the project to record key efficacy and safety parameters independent of the eCRFs) may include subject hospital/clinic records, physician's and nurse's notes, appointment book, original laboratory reports, ECG, electroencephalogram, X-ray, pathology and special assessment reports, signed ICFs, consultant letters, and subject screening and enrollment logs. The Investigator must keep these 2 categories of documents on file for at least 2 years following the marketing application approval date for the study drug and for the indication being investigated or for 2 years after the investigation is discontinued and the FDA notified. After that period of time, the documents may be destroyed subject to local regulations with prior written permission from Kadmon Corporation. If the Investigator wants to assign the study records to another party or move them to another location, Kadmon Corporation must be notified in advance.

If the Investigator cannot guarantee the archiving requirement at the study site for any or all of the documents, special arrangements must be made between the Investigator and Kadmon Corporation to store these in a sealed container outside of the study site so that they can be returned sealed to the Investigator in case of a regulatory audit. When source documents are required for the continued care of the subject, appropriate copies should be made for storing outside of the study site.

14.2 SOURCE DOCUMENTS AND BACKGROUND DATA

Upon request, the Investigator will supply Kadmon Corporation with any required background data from the study documentation or clinic records. In case of special

problems or governmental queries or requests for audit inspections, it is also necessary to have access to the complete study records, provided if subject confidentiality is protected.

14.3 AUDITS AND INSPECTIONS

Kadmon Corporation, LLC

The Investigator should understand that source documents for this study should be made available to appropriately qualified personnel from the Kadmon Corporation Quality Assurance Unit (or designee) or to health authority inspectors after appropriate notification. The verification of the eCRF data must be by direct inspection of source documents.

14.4 ELECTRONIC CASE REPORT FORMS

Clinical trial data for this study will be captured on electronic eCRF. The Investigator agrees to provide all information requested on the eCRF in an accurate manner according to instructions provided. Electronic CRFs are designed for computer processing and analysis. The Investigator should ensure the accuracy, completeness, and timeliness of the data reported to Kadmon Corporation (or designee) in the eCRF and in all required reports.

An eCRF is required to be submitted for every subject who receives any amount of study drug. This includes submission of retrievable data on subjects who withdraw before completion of the study. The eCRFs must be reviewed for completeness and accuracy, and electronically signed where indicated, by the Principal Investigator or authorized delegate from the study staff. If a subject stops treatment or terminates from the study, the dates and reasons must be noted on the eCRF.

27 May 2021

15. MONITORING OF THE STUDY

It is understood that the responsible monitor (or designee) will contact and visit the Investigator regularly and will be allowed on request to inspect the various records of the trial (eCRFs and other pertinent data) provided if subject confidentiality is maintained in accordance with local requirements.

It will be the monitor's responsibility to inspect the eCRFs at regular intervals throughout the study, to verify the adherence to the protocol and the completeness, consistency, and accuracy of the data being entered on them. The monitor should have access to laboratory test reports and other subject records needed to verify the entries on the eCRF. The Investigator (or designee) must agree to cooperate with the monitor to ensure that any problems detected in the course of these monitoring visits are resolved.

16. CONFIDENTIALITY OF TRIAL DOCUMENTS AND SUBJECT RECORDS

The Investigator must ensure that subjects' anonymity will be maintained and that their identities are protected from unauthorized parties. On eCRFs or other documents submitted to Kadmon Corporation, subjects should be identified by an identification code and not by their names. The subjects' personal information should be redacted on all source documents prior to submission to Kadmon Corporation (or designee). The Investigator should keep a subject enrollment log showing codes, names, and addresses. The Investigator should maintain documents not for submission to Kadmon Corporation (e.g., subjects' written consent forms) in strict confidence.

17. PUBLICATION OF DATA AND PROTECTION OF TRADE SECRETS

The results of this study may be published or presented at scientific meetings. The Investigator agrees to submit all manuscripts or abstracts to Kadmon Corporation for review at least 30 days before submission. This allows Kadmon Corporation to protect proprietary information and to provide comments based on information from other studies that may not yet be available to the Investigator.

In the event that Kadmon Corporation coordinates a publication or presentation of study results from all study sites, the participation of Investigator or other representatives of study site as a named author shall be determined in accordance with Kadmon Corporation policy and generally accepted standards for authorship.

19. APPENDIX A: SCHEDULE OF ASSESSMENTS

Schedule of Assessments (continued on next page)																		
		Double-Blind Treatment Period (28 Weeks)							Open-Label Treatment Period (24 Weeks)									
Assessment	Screening Visit	Week 1 (Baseline)	Day 15	End of Week 4	End of Week 8	End of Week 12	End of Week 16	End of Week 20	End of Week 24	End of Week 28°	End of Week 32	End of Week 36	End of Week 40	End of Week 44	End of Week 48	End of Week 52/ EOT	28-Day Safety	Unscheduled
Study Day	-29 to -1	1	15 (±3 days)	29 (±3 days)	57 (±3 days)	85 (±3 days)	113 (±3 days)	141 (±3 days)	169 (±3 days)	197 (±3 days)	225 (±3 days)	253 (±3 days)	281 (±3 days)	309 (±3 days)	337 (±3 days)	365 (±3 days)	Follow- Up (±3 days)	Visit
Informed consent ^a	X																	
Subject Demography	Х																	
Medical history	X																	
Inclusion/Exclusion Criteria	X	х																
Randomization ^b		Х								X								
EFFICACY ASSESSMENTS																		
CRISS ^c					X		X		X	X		X		X		X	X	X
mRSS ^d	X	X			x		X		X	X		X		X		X	X	X
FVC ^d	X				x		X		X	X		X		X		X		
SHAQ-DI ^d		Х			x		X		X	X		X		х		X	X	X
Physician global assessment ^d		х			х		х		х	х		х		х		х	х	х
Patient global assessment ^d		х			х		х		х	х		х		х		х	х	Х
PFTs ^e		X							X							X	X	X
HRCT ^f		Х							Х							X ^f		
Schedule of As	sessment	s (conti	nued)															
	Double-Blind Treatment Period (28 Weeks)							Open-Label Treatment Period (24 Weeks)										

Kadmon Corporation, LLC 27 May2021

	Screening Visit	Week 1 (Baseline	Day 15	End of Week 4	End of Week 8	End of Week 12	End of Week 16	End of Week 20	End of Week 24	End of Week 28°	End of Week 32	End of Week 36	End of Week 40	End of Week 44	End of Week 48	End of Week 52 / End of Treatme nt	28-Day Safety Follow-	Unscheduled Visit
Study Day	-29 to -1	1	15 (±3 days)	29 (±3 days)	57 (±3 days)	85 (±3 days)	113 (±3 days)	141 (±3 days)	169 (±3 days)	197 (±3 days)	225 (±3 days)	253 (±3 days)	281 (±3 days)	309 (±3 days)	337 (±3 days)	365 (±3 days)	Up (±3 days)	
Skin Biopsies ^g		X							X							X		
Pharmacokinetics ⁿ				X	X													
Pharmacodynamics ^m		X			X				X							X		
SAFETY ASSESSMENTS																		
Complete PEh	X	X							X	X						X	X	X
Symptom-directed PE ^h			X	X	X	Х	Х	X			Х	X	X	X	X			
Vital signs ⁱ	X	X	X	X	X	x	x	X	X	X	x	X	X	X	X	X	X	X
Weight	X	X	X	X	X	X	X	X	X	X	X	X	X	X	X	X	X	X
Hematology and chemistry ^j	X	х	х	х	х	x	x	х	х	х	х	х	х	х	х	х	X	х
Urinalysis		X	X	X	X	X	X	X	X	X	X	X	X	X	X	X	X	X
12-Lead ECG	X	X	X	X	х	x	x	X	X	X	x	X	X	X	X	X	x	X
Pregnancy Test ^k	X	X	X	X	X	X	X	X	X	X	X	X	X	X	X	X	X	X
Study diary (dispense/collect)		х		х	х	Х	Х	Х	Х	Х	х	х	Х	х	Х	х		х
Study drug administration ¹		х	X	x	x	x	x	х	Х	Х	х	х	Х	х	Х			х
Dispense/Collect study drug ¹		х		х	х	х	х	х	X	X	х	х	X	х	X	x		х
Concomitant																		

Abbreviations: CRISS = Combined Response Index in Diffuse Cutaneous Systemic Sclerosis; ECG = electrocardiogram; EDC = electronic data capture; EOT = End-of-Treatment; FVC = forced vital capacity; HRCT = high-resolution computerized tomography; ICF = informed consent form; ILD = interstitial lung disease; mRSS = modified Rodnan Skin Score; PE = physical examination; PFT = pulmonary function test; SHAQ—DI = Scleroderma Health Assessment Questionnaire—Disability Index

The ICF must be signed before any study procedure begins.

Medications

Adverse Events

Kadmon Corporation, LLC

Page 86 of 99

27 May 2021

To be collected from the date that the ICF is signed until 28 days after last dose of Belumosudil.

[figure not shown]
- b. Re-randomization of the placebo group to one of two arms will take place after the un-blinding procedures take place.
- c. CRISS will not be performed on site, but rather will be calculated outside of EDC.
- d. mRSS, SHAQ-DI, FVC, physician global assessment and patient global assessment will be performed at baseline Day 1, Day 57, Day 113, Day 169, Day 197, and then every 8 weeks thereafter until Week 52. In addition, after their last dose of study drug (4-Week Follow-Up Visit). mRSS and FVC will also be performed at screening as one of the inclusion criteria. FVCs should be performed if PFT is not performed at the same visit.
- e. HRCT and PFTs, to include FEV₁, FVC, DL_{CO} (corrected for Hb), TLC, and RV, will be performed at baseline, Day 169, and Day 365 (each ± 7 days). In addition, PFTs will be performed after their last dose of study drug (4-Week Follow-Up Visit). If the HRCT or PFTs is performed within one month of the EOT visit, it does not need to be done again at the EOT visit.
- f. HRCT will be done only in subjects at Day 1, Day 169, and Day 365 (each ± 7 days) if they have confirmed ILD at baseline. This is not required at the End of Treatment visit.
- g. Double punch Skin biopsies are MANDATORY for all subjects on Day 1 and Day 169 and Optional on Day 365 and will be obtained from the dorsal mid-forearm for Gene Profiling. This assessment is not required for End of Treatment.
- h. A complete PE is to include documentation of height (screening only), weight, body temperature, and vital signs (blood pressure [sitting], pulse rate [sitting], and respiratory rate) and will be performed by a physician or staff member who is qualified to perform such examinations (e.g., physician assistant, nurse practitioner). All PEs, whether complete or symptom-directed, will include assessment of cardiac (including heart rate and vital signs), musculoskeletal (i.e., muscle aches), and neurological (i.e., gait) systems. A complete PE include will include evaluation of primary endpoints.
- i. Sitting blood pressure, heart rate to be obtained (after 5 minutes of rest)
- j. See Section 6.2.4 for a complete list of laboratory safety assessments. If increases in liver enzymes are observed at any time in a subject, refer to Section 4.13.
- k. Women of childbearing potential must have a negative urine pregnancy test. Positive results are to be confirmed with serum testing.
- 1. Subjects will take their morning dose at the clinic and then will be dispensed study drug for home administration.
- m. Pharmacodynamics will be collected as follows: within 60 minutes pre-dose at baseline, Week 8, week 24, and Week 52. ELFT collected at Baseline, Week 8, Week 24 and Week 52.
- n. Pharmacokinetics will be collected within 60 minutes pre-dose of dosing and 3 hours post-dose with a window of 10 minutes at Week 4 and Week 8.
- o. All subjects will be un-blinded at this visit.

Note: At Week 1, Day 1 visit, if screening was completed within 7 days of baseline, only the complete PE and vital sign measurements need to be repeated.

Note: The term EOT refers to early withdrawal or Week 52, as appropriate.

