1.3 BELUMOSUDIL NONCLINICAL EXPERIENCE

In vitro, belumosudil has demonstrated an impact on the T-helper 17 (Th17) and regulatory T cells (Treg)-immune responses as well as on the actin/myosin cytoskeletal network and collagen formation. In vivo, belumosudil has demonstrated efficacy in a variety of clinically relevant animal models of disease including chronic graft versus host disease (cGVHD), scleroderma, idiopathic pulmonary fibrosis (IPF), and other autoimmune diseases.

Good Laboratory Practice (GLP) compliant rat and dog general toxicology/toxicokinetic studies of acute, sub-chronic (1-and 3-month), and chronic (6-month rat and 9-month dog) duration have been completed. In addition, safety pharmacology (human ether-à-go go related gene [in vitro], central nervous system [rat], respiratory [rat], and cardiovascular [dog]), embryo-fetal toxicology [rat and rabbit], male/female fertility [rat]), genotoxicity, and phototoxicity studies have also been completed. The primary nonclinical toxicology finding at/near clinically relevant exposures were limited to changes in the cardiovascular (blood pressure lowering), hepatic (transaminitis, hypertrophy/increased organ weight, and cholestasis/inflammation), renal (increased blood urea nitrogen [BUN], tubular changes, pigmentation, intracellular protein droplets in the epithelium), gastrointestinal (decreased appetite), and hematopoietic/immunologic (anemia with regeneration and thymic/splenic lymphoid depletion) systems.

Belumosudil demonstrated embryo-fetal toxicity/teratogenicity as well as reduced male fertility (reduced fertility index/sperm concentration/motility and increased abnormal sperm percentage), and changes in the testes/epididymis (decreased organ weights and degenerative histopathology). Male fertility findings were generally at higher than clinically relevant exposures.

All pivotal non-clinical safety studies (i.e., those studies identified in International Conference on Harmonization guidelines as needing to be conducted in accordance with GLP) were conducted in a country that is a member of the Organisation for Economic Cooperation and Development (OECD) Mutual Acceptance of Data program in accordance with the OECD Test Guidelines and Principles of GLP. Study details and potential clinically relevant findings from these studies are summarized in the Belumosudil Investigator's Brochure.

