3.4 INCLUSION CRITERIA

- Male and female subjects ≥ 18 years old with the diagnosis of dcSSc according to the 2013 American College of Rheumatology and European League Against Rheumatism criteria
- 2. Must have disease duration (defined as interval from first non-Raynaud disease manifestation) of ≤ 5 years
- 3. Must have mRSS of \geq 15 but \leq 35
- 4. Active disease defined as any of the following within the 6 months prior to screening:
 - a. Increase in mRSS by ≥ 3 units
 - b. Increase in mRSS by ≥ 2 units with involvement of 1 new body area
 - c. Involvement of 2 new body areas

Page 33 of 99

27 May 2021

- d. Symptoms indicative of skin activity such as severe cutaneous itching or burning
- 5. Subjects receiving concomitant immunosuppression must be on a stable dose for at least 3 months prior to screening
- 6. Adequate organ and bone marrow functions evaluated during the 28 days prior to enrollment as follows:
 - a. Absolute neutrophil count $\geq 1.5 \times 10^9/L$
 - b. Platelet count $\geq 100 \times 10^9/L$
 - c. Total bilirubin $\leq 1.0 \times$ upper limit of normal (ULN)
 - d. Alanine aminotransferase (ALT), aspartate aminotransferase (AST), and serum creatinine $\leq 1.5 \times ULN$
- 7. Female subjects of childbearing potential have a negative pregnancy test at screening. Females of childbearing potential are defined as sexually mature women without prior hysterectomy or who have had any evidence of menses in the past 12 months. However, women who have been amenorrheic for 12 or more months are still considered to be of childbearing potential if the amenorrhea is possibly due to prior chemotherapy, anti-estrogens, or ovarian suppression.
 - a. Women of childbearing potential (i.e., menstruating women) must have a negative urine pregnancy test (positive urine tests are to be confirmed by serum test) documented within the 24-hour period prior to the first dose of study drug.

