3.6 SCREENING

The screening period commences once the ICF is signed. Adequate time must be allowed for the subject to ask questions and make a voluntary decision. The ICF must be signed before any study-specific samples are taken or study-specific tests or evaluations are conducted.

Data regarding screen-failures will be captured in the electronic data capture (EDC) system.

Screening assessments as summarized in the Schedule of Assessments (Appendix A) will be performed within 29 days of first dose of study drug (Week 1, Day 1 visit).

Study eligibility will be based on satisfying all of the study inclusion and exclusion criteria.

Re-screening of subjects will be allowed only upon approval of the Medical Monitor.

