5.2.1 Week 1, Day 1 Visit (Baseline)

At the Week 1 Day 1 visit, subjects will come to the clinic to have the following procedures:

- Confirmation of inclusion/exclusion criteria
- Randomization
- mRSS
- SHAQ-DI
- Physician Global Assessment
- Patient Global Assessment
- Pulmonary function test (PFT)*
- HRCT (± 7 days; for subjects with ILD at screening only)
- Skin biopsies
- Sampling for PD
- Complete PE
- Vital signs
- Weight
- Hematology and chemistry*
- Urinalysis*
- 12-lead ECG
- Pregnancy test
- Dispense study diary
- Study drug administration review with patient
- Dispense study drug
- Concomitant medication assessment
- AE assessment

*If these assessments were conducted within seven (7) days of baseline, they do not need to be repeated.

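### Read literally, an Appendix A note waives the Day 1 pregnancy test and ECG, against Section 5.2.1 and, for the pregnancy test, against the 24-hour rule in criterion 7a

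*Protocol*

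**What the plan says.** Four parts of the protocol govern what has to be done on Day 1.

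- **Appendix A, closing note on the Week 1, Day 1 visit.** Its condition is "if screening was completed within 7 days of baseline". Its consequence is that "only the complete PE and vital sign measurements need to be repeated". It names no exceptions.
- **Section 3.4, criterion 7a (also in the synopsis).** Women of childbearing potential need a negative urine pregnancy test "documented within the 24-hour period prior to the first dose of study drug".
- **Section 5.2.1.** The Day 1 list includes "Pregnancy test", the 12-lead ECG and mRSS, none of them starred. The footnote "If these assessments were conducted within seven (7) days of baseline, they do not need to be repeated" applies only to the starred items: PFTs, hematology and chemistry, and urinalysis.
- **Appendix A grid and footnotes.** The grid marks the pregnancy test, ECG and mRSS at Week 1. Footnote d says "mRSS, SHAQ-DI, FVC, physician global assessment and patient global assessment will be performed at baseline Day 1". Footnote h counts evaluation of the primary endpoints as part of a complete physical examination (PE). Footnote k asks for a negative urine test but gives no time window.

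Section 1.3 supplies the safety context: "Belumosudil demonstrated embryo-fetal toxicity/teratogenicity".

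**The concern.** Two provisions allow Day 1 work to be skipped on the strength of recent screening, and they differ in scope. Section 5.2.1 names three items. The Appendix A note exempts everything except two. A site that takes the note at its word would omit tests that Section 5.2.1 requires and, for the pregnancy test, would miss the window set by an eligibility criterion.

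The main stake is subject safety: a first dose given on a pregnancy test older than criterion 7a permits. The second is the ECG. QTcF is an exclusion criterion (Section 3.5), and its change from baseline is a safety endpoint (Section 6.2.1; SAP Section 3.9.4), so whether a Day 1 ECG exists should not depend on which part of the protocol a site follows. A third, less certain, stake is the mRSS baseline, because mRSS enters CRISS.

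**Working it through.** The plan states no figure to reproduce. The check is a comparison of texts plus one subtraction.

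**Step 1: what the note can reach.** It speaks of repeating, so it reaches only procedures already done at screening (Section 5.1). SHAQ-DI, the two global assessments, full PFTs, HRCT, biopsies, PD sampling and urinalysis are not on the screening list, so the note is not naturally read as waiving them. Concomitant medications and adverse events are recorded continuously from consent, so I leave them out.

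**Step 2: compare the procedures done at both visits.**

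| Procedure | 7-day carry-over in Section 5.2.1? | Repeat required by the note? | Conflict |
|---|---|---|---|
| Complete PE, vital signs | No | Yes | None |
| Weight | No | Yes, as part of the PE (footnote h) | None |
| Hematology, chemistry | Yes | No | None |
| Pregnancy test | No | No | Yes, and with criterion 7a |
| 12-lead ECG | No | No | Yes |
| mRSS | No | Unclear (footnotes d and h) | Unclear |

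**Step 3: size of the pregnancy-test conflict.**

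- Oldest test under the note: 7 days × 24 h = 168 h.
- Oldest test under criterion 7a: 24 h.
- Difference: 168 − 24 = 144 h, or 6 days.

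The two rules agree only when the screening test happens to fall within 24 hours of the first dose. Footnote k does not settle the matter, since it has no window and no exception to the note.

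**Step 4: ECG.** No separate eligibility window applies, so the conflict is between the note and Section 5.2.1 alone. If the Day 1 ECG is omitted, SAP Section 3.1.6 takes the last value within 29 days before first dose. The QTcF baseline would then be the screening ECG.

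**Step 5: mRSS.** Footnote d puts mRSS at Day 1, with screening as an additional assessment. Footnote h brings primary-endpoint evaluation into the complete PE, which the note keeps. Both suggest that mRSS is still required, although the note does not say so. If a site did omit it, the SAP's baseline rule would accept the screening value. The documents give no figure for how much mRSS varies over 7 days, so the effect cannot be sized.

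**The case against.** The strongest reply is that the protocol already guards against the harm. The note sets a minimum and forbids nothing, so a site that performs the Day 1 pregnancy test, ECG and mRSS complies with the note, Section 5.2.1 and criterion 7a at once. Criterion 7a is an eligibility condition, Section 3.6 rests eligibility on meeting all criteria, and eligibility is confirmed again on Day 1 in both Section 5.2.1 and the Appendix A grid. Section 6.2.5 also presumes a urine test at baseline. Dosing on a week-old test would mean breaching criterion 7a and missing the breach at that check.

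All of this stands, and it limits the point. It does not remove it: the note's wording is unqualified, and it permits omissions that Section 5.2.1 does not.

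A reader might infer three stronger things that the documents do not support.

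- *That the passages cannot all be followed.* They can, by doing every Day 1 test.
- *That the note removes the Day 1 mRSS and so disturbs the primary endpoint.* Footnotes d and h point the other way, and the SAP has a defined baseline rule.
- *That most of the trial is exposed because Section 1.1 puts women at 80%–90% of systemic sclerosis patients.* Applied to 60 subjects this gives 0.80 × 60 = 48 to 0.90 × 60 = 54 women. That is a population figure, not this trial's enrolment. It also includes women not of childbearing potential, women on placebo, and women screened more than 7 days before Day 1, to whom the note does not apply.

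**Conclusion.** The point holds as a conflict between operative passages. The Appendix A note, read literally, waives the Day 1 pregnancy test and ECG, which Section 5.2.1 does not allow to be carried over. For the pregnancy test it also departs from criterion 7a: up to 168 hours against at most 24.

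The 7-day figure assumes that the screening tests are done at one visit, as Section 5.1 describes. The note turns on when screening was completed, and Section 3.6 lets screening assessments be "performed within 29 days of first dose of study drug". If screening were spread over that window, the note by itself would not hold the test's age to 7 days.

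The number of subjects affected cannot be derived from the documents. The mRSS question is an ambiguity to clear up, with a probably small effect on baseline. The issue deserves correction because it touches a safety criterion for a drug with reported embryo-fetal toxicity. It does not call the efficacy analysis into question.

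**What to change.** Reconcile the Appendix A note with criterion 7a (Section 3.4 and the synopsis), Section 5.2.1, and Appendix A footnotes d and h, so that together they give one list of what may be carried over from screening. State in the note how the pregnancy test, the 12-lead ECG and mRSS are handled. Which rule stands is for the sponsor to decide.

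The cost is about one sentence in Appendix A. The three procedures are already scheduled at Day 1, so no new assessment is needed.
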